We will perform a formative evaluation and mapping of existing local services for young adults with diabetes at Newham University Hospital e.g. number of new/existing patients per year, appointment frequency, attendance rates, questionnaire-based assessment of experience and acceptability, service-level and patient-centred outcomes, numbers of patients with type 1 vs. type 2 diabetes and number of patients using continuous subcutaneous insulin infusion (pump) therapy and uptake of structured education. This process will allow us to contextualise the co-design process and implementation of the group-based intervention.

The formative evaluation will occur at 3 units delivering diabetes care to young adults:

- Newham University Hospital: where the proposed project is centred and the co-designed new care model of group clinics for young adults with diabetes will take place
- Whittington Hospital NHS Trust: a comparison unit delivering diabetes care to young adults, in a clinic led by [name], Consultant Diabetologist
- Royal London Hospital: a comparison unit delivering diabetes care to young adults, in a clinic led by [name]

Delivery: The researcher-in-residence will have a central role, supported by other members of the research team, in the realist review, survey and mapping exercise, in particular ensuring that the voice of service partners influences these scoping activities. At this stage, draft logic models and associated theories of change will be prepared.

Process: as above

Anticipated outputs:

- Publication of a realist review of the evidence for group clinics in diabetes in a peer-reviewed journal
- Results of national scoping exercise and formative evaluation of local services to feed into Workstreams 2 and 5 (co-design and dissemination)

Workstream 2: Co-design of a group clinic-based care model

Operational objective: To use experience-based co-design to design a group clinic-based care model that meets the complex needs of young adults with diabetes within their socio-cultural context

Timescale: Q2-3, Q6-7

Methodological approach: The involvement of service users and staff in the co-design of all stages of this project is essential for ensuring that the new group clinic-based care model meets the needs of its users and that its implementation within existing care pathways is feasible. Early involvement of service users and staff in the design of new services ensures that the outcomes from it are more likely to meet the needs of patients and increases the likelihood that it will succeed. The formal process behind this early service user and staff involvement, 'Co-design' contributes to building the support and confidence of staff, patients and the wider public and has been shown to make research more relevant and more widely disseminated (26). Methods for co-designing clinical services vary, but we propose to use the Experience-Based Co-Design model (14) with adaptations for our specific client group (young adults with diabetes). EBCD draws together qualitative experiences of patients and staff, via in-depth interviewing, observations and group discussion; staff and patients then work together to identify the priorities for service development. The EBCD process is iterative, allowing ongoing redesign and adaptation throughout the process of implementing the new service. Whilst the group clinics that are designed through EBCD will have a bespoke design, tailored to their participants and setting in Newham, the process of co-design and implementation of group clinic-based diabetes care arising from it will be will be generalisable to wider contexts and patient groups.

Setting: Community-based facilities in the London Borough of Newham, a deprived, ethnically diverse population with a high prevalence of long-term conditions and reduced life expectancy compared to UK averages.

Participants: Young adults with diabetes, staff and relevant stakeholders (n=15-20)

Delivery: The co-design element of our group clinic intervention will be coordinated by the Association of Young Peoples' Health, whose staff have experience of these processes as well as of working with service users (patients and their families) and staff members involved in delivering their care. The researcher-in-residence will embed academic expertise within the process of intervention design and, with the support of the project steering group, will guide the interaction between co-design and qualitative evaluation of the implemented group clinics. The embedded researcher will participate in all of the EBCD meetings and use results of the scoping exercise and systematic review in workstream 1 to consolidate the evolving co-designed model within relevant conceptual frameworks and theories. In doing so, the embedded researcher will negotiate the evidence, needs and requirements of the new care model and facilitate a consensus view about the most appropriate intervention design.

The co-design process will have two concentrated phases, an initial phase of co-design 'from scratch' during Q2+3, and a second 'revision' phase during Q6+7. The co-design revision phase will occur after the new care model for young people with diabetes have been implemented and will involve the patient and staff members involved in the initial co-design process, as well as new members. All co-design will be facilitated by AYPH, with close input from the researcher-in-residence and supervision from the project steering group.

The project steering group will provide regular supervision of the entire co-design process, its interaction with the planned evaluation (workstream 4) and dissemination activities (workstream 5). Service users and staff involved in the EBCD process will be encouraged to become involved in dissemination activities.

Process: See Gantt chart.

Anticipated output:

• Co-designed new model of group-based care for young adults with diabetes.

Workstream 3: Implementation of the group clinic-based care model

Operational objective: Implement the co-designed group clinic-based care model

Timescale: Q3-10

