- Workstream 3: Implementation of the group clinic-based care model, resulting in the delivery of a codesigned group clinic-based model of care to young adults with diabetes.
- Workstream 4: Evaluation of the group clinic-based care model, employing an innovative Researcher-in-Residence to conduct a rigorous test of how the group clinics work in practice, and to identify their active ingredients, mechanisms of action, enablers and constraints. The evaluation of these group clinics will follow qualitative methodology and will be guided by the findings of the initial realist review. Evaluation will also include a detailed analysis of how and to what extent our findings may be generalisable to other patients group and settings. Quantitative analysis will indicate the potential for group clinics to improve clinical outcomes and patient engagement and/or reduce care costs, by comparison of national audit data and benchmarking against other centres delivering care to young adults with diabetes. This analysis will inform the future design of a cluster-randomised clinical trial of group clinics for young people with diabetes to generate definitive quantitative clinical and health economic outcomes.
- Workstream 5: Dissemination, in order to share the findings with participants, user groups, local staff, the wider stakeholder group, the academic community and policy makers, strategic decision makers and funders.

The project will be managed in teams closely aligned to each workstream, and with an overarching project advisory group. In addition, patient and public involvement is central to the development, implementation, evaluation of and dissemination from of this project.

Background and Rationale - why this research is needed now

1. Current practice of diabetes care and who/what it fails to reach

This proposed research is important for people who have diabetes and for the NHS for a number of reasons. First, many young adults with diabetes report poor experience of transition from paediatric to adult care, dissatisfaction with the care they receive and poor engagement with self-management. These findings are reflected in low clinic attendance rates and poor outcomes compared to young adults in other EU countries, in contrast to the UK's good performance in diabetes care overall. Second, there is an urgent need for new care models that use resources more efficiently while ensuring that a high level of patient experience and clinical outcomes are maintained.

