- To conduct a comparative evaluation of the model against current standard care at Newham University Hospital, in order to elucidate patient and provider perceptions and mechanisms of action. To analyse and compare quantitative data on care processes, outcomes and costs from the new care model for young adults in Newham against national benchmark data (from the National Diabetes Audit) and against data from two other comparable local diabetes services (at Royal London and Whittington Hospitals). To use this quantitative analysis to guide the design of a future cluster-randomised clinical trial to determine clinical and health economic outcomes (workstream 4)
- To disseminate the outcomes of our scoping and realist review, the co-designed new care model and its evaluation to service users and relevant stakeholders and generalise them to a wider context (workstream 5)

Research Questions

- Could an innovative new group clinic-based care model meet the complex health and social needs of young people with diabetes? (workstream 1+2)
- Could this new care model be a better way of promoting diabetes self-management than traditional care (workstreams 1+2)? If so, what do the experiences of participants, the functioning of the group, and the wider context in which the new model takes place tell us about its active ingredients? (workstream 3+4)
- What are the feasibility, acceptability, costs and impact on outcomes of introducing these group clinics for their
 users and stakeholders, and what is the organisational impact to the NHS and other stakeholders of this model?
 (workstreams 3,4+5)
- What would be the optimal size and study design of a cluster-randomised controlled study to evaluate the clinical benefit and costs of offering group clinics to all young adults with diabetes? What other factors should be considered when planning such a RCT (e.g. factors relating to patient characteristics, existing models of service delivery, acceptability and mechanisms of actions of group clinics on clinical outcomes)? (workstreams 3,4+5)

Anticipated outputs

• A realist review on the evidence of group clinics in diabetes.

- A co-designed group-based new model of care that meets the needs of young adults with diabetes.
- An enhanced understanding of the role of experience-based co-design in redesigning conventional NHS services to better meet the health and social care needs of specific hard-to-reach groups with long-term conditions.

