- Does the need for close integration with other health care providers, e.g. primary care, impact the feasibility and costs associated with delivering the new care model?

Quantitative evaluation - general principles

A range of quantitative data (clinical, process-driven and economic) will be collected and analysed as part of a mixed methods evaluation in this project. However, definitive evaluation of the impact of group clinics is not possible within this study for several reasons. First, the intervention is not yet sufficiently developed; the intervention will be codesigned at the beginning of the study period; it will then be refined and improved throughout the remainder of the study period. Second, the timescale of our study is not long enough to evaluate the full impact of new behaviours such as increased exercise, diet changes, clinic attendance. Third, our study focuses on in-depth analysis of a relatively small group of patients, so is not powered to detect a small/moderate effect of group clinics. For example, to show a statistically significant improvement in HbA1c results in the 214 patients attending the young adult clinic, the average HbA1c result would have to decrease from 68 to 57mmol/l for people with Type 2 diabetes, and 86 to 79mmol/l for those with Type 1 diabetes; we do not think is a realistic goal within the timeframe of this project. Lastly, there is uncertainty about the most appropriate outcome measures with which to evaluate impact (i.e. we do not know whether traditionally-used outcome measures for diabetes studies will be the most relevant for these populations and for the anticipated effects of this intervention).

With these limitations in mind, the quantitative analysis will instead focus on:

- Detailed, descriptive comparisons of clinical and service-based outcomes in Newham before/after the introduction of group clinics for young adults.
- Comparison of clinical and service-based outcomes (i) at unit level, between comparable services at Newham University Hospital, the Royal London Hospital and the Whittington Hospital, and (ii) at national level, using National Diabetes Audit data to understand heterogeneity and generalisability.
- Assessing the feasibility of collecting clinical, process and cost data at patient- and unit-level to enable the design of a future cluster randomised controlled trial.

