
• Resource use: resource inputs associated with the implementation of group clinics will be recorded on specifically designed staff- and researcher-completed logs. We will measure all relevant staff contact and non-contact time e.g. for delivery of and participation in staff training, group clinic delivery to patients and time take for other associated activities such as note writing. We will also record patient attendance rates at the level of groups and patients. Given the potential complexity of this data collection, we will seek feedback on the design of the logs from a sample of those who will be expected to complete them, provide accompanying written guidance for reference (and training where feasible) on their completion and check completeness and quality of data on an ongoing basis. Broader resource us data related to use of other core services will be extracted from patient records.

Data analysis: there will be two types of quantitative analysis of clinical outcomes and patient activation:

- Intention to treat: simple descriptive statistics will be used to compare clinical outcomes among young adults with diabetes attending the group clinics with controls from the same clinic over the previous year.
- Comparison of baseline characteristics, clinical outcomes and patient activation among patients who receive the intervention (n=80-100) with control data participants (n=60). The first stage of this process will complement the qualitative findings into which patients are most attracted by the idea of group clinics. We will compare baseline socio-demographic and clinical characteristics of those who accept versus those who decline the opportunity to participate in group clinics. We will then use longitudinal data to compare the trajectories of clinical and activation measures over the following year for individuals in the accept vs. decline groups (difference in difference analysis).

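### The protocol draws on hospital and national benchmarking to indicate what group clinics can achieve, elsewhere limits the same comparison to description, and states no change-from-baseline contrast between units

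*Protocol*

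**What the plan says.** The protocol gives this comparison two different purposes.

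**Indicating potential.** The workstream 4 item in the opening summary says "Quantitative analysis will indicate the potential for group clinics to improve clinical outcomes and patient engagement and/or reduce care costs", and names the means: "by comparison of national audit data and benchmarking against other centres delivering care to young adults with diabetes". The workstream 4 operational objective sets data obtained under the new model in Newham against the national audit and "against data from two other comparable local diabetes services", the Royal London and the Whittington.

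**Describing units.** The section on general principles of the quantitative evaluation lists a comparison "at unit level, between comparable services at Newham University Hospital, the Royal London Hospital and the Whittington Hospital" and a second one "at national level, using National Diabetes Audit data to understand heterogeneity and generalisability". The workstream 4 data analysis section gives the external comparison three uses: testing whether unit-level data can be collected, identifying case-mix differences, and characterising outcomes under different units.

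**Where change over time appears.** A before/after comparison is listed for Newham only. The one difference-in-difference analysis named is for "individuals in the accept vs. decline groups (difference in difference analysis".

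**What baseline exists.** Workstream 1 (Q1-Q2) contains a formative evaluation whose example items include attendance rates and service-level outcomes. Its opening sentence, and the workstream 1 method list, mention Newham only. The text then says "The formative evaluation will occur at 3 units delivering diabetes care to young adults" and names Newham, the Whittington and the Royal London. Implementation (workstream 3) runs Q3-10.

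**The concern.** If Newham under group clinics is set beside hospitals without them, and the gap is used to indicate what group clinics can do, the gap contains everything that already separated the hospitals: catchment, case mix, booking practice and clinic organisation. The protocol's own background makes such differences likely, at least against the national benchmark. It reports a deprivation index of 42.9 for Newham, diabetes prevalence of 9.4% against 4-7% nationally, and a 68% non-White population. Newham could look worse than its comparators although group clinics help, or better for unrelated reasons.

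The protocol's caveat that no definitive evaluation is possible rests on the immaturity of the intervention, the short timescale, limited power and uncertainty about outcome measures. It does not address bias from standing differences. A contrast that removes the stable part of that bias appears to be within reach but is not stated. The result is meant to inform a future cluster-randomised trial and publications on the potential of group clinics.

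**Working it through.** **1. The protocol's own figures.** No precision or effect size is given for the unit-level or national comparison. The only numerical statement is the HbA1c fall needed for significance in the 214 clinic patients (68 to 57 in Type 2, 86 to 79 in Type 1). It cannot be reproduced without the SD, power, significance level and diabetes-type split, and this point does not depend on it.

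**2. The contrasts side by side.**

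| Comparison | Change over time stated? | Stated purpose |
|---|---|---|
| Newham before/after | Yes | Descriptive |
| Accept vs decline | Yes (difference in difference) | Trajectories over the following year |
| Newham vs other units | No | Potential (summary, objective); heterogeneity, case mix, feasibility (principles, data analysis) |
| Newham vs national audit | No | As above |

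**3. How far could group clinics move a unit-level rate?** Inputs: Newham non-attendance 28% (workstream 4, data collection); 80-100 group-clinic participants (workstream 3); 214 young adult clinic patients (general principles). Assumptions: equal appointments per patient, and a relative fall *r* among participants only.

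Shift in unit rate = 28 × *r* × (participants / 214)

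- Share reached: 80/214 = 37%; 100/214 = 47%.
- *r* = 25%: 28 × 0.25 × 80/214 = 2.6 points; 28 × 0.25 × 100/214 = 3.3 points.
- *r* halved to 12.5%: 1.3 to 1.6 points.
- *r* doubled to 50%: 5.2 to 6.5 points.
- Ceiling, with all non-attendance among participants abolished: 28 × 80/214 = 10.5 to 28 × 100/214 = 13.1 points.

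**4. What a level comparison shows.** Observed gap = standing gap + shift. With a shift of -2.6 to -3.3 points, an adverse standing gap above 3.3 points makes Newham look worse despite a real benefit. A favourable gap of 3 points gives an observed difference of 5.6 to 6.3 points, about double the true shift.

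**5. Case mix and HbA1c.** The Newham means are 86 (Type 1) and 68 (Type 2), a difference of 18. If these means applied at every unit (assumption), each 10-percentage-point difference in Type 1 share would move a unit mean by 0.10 × 18 = 1.8 with no intervention effect.

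**6. What differencing does.** The contrast is (Newham after - Newham before) - (comparator after - comparator before). A constant gap cancels; differential drift does not. For measures repeated on the same patients, the standard error relative to a level comparison is √(2(1 - ρ)), where ρ is the before/after correlation. This is 1 at ρ = 0.5, √0.6 = 0.77 at ρ = 0.7, and above 1 when ρ is below 0.5.

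**The case against.** The strongest defence is that the detailed sections govern. There the comparison serves heterogeneity, feasibility and case mix, and for those purposes standing differences between hospitals are what is sought. This stands, and it is why the level comparisons must stay.

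A reader might infer that the protocol commits itself to comparing levels and will read hospital gaps as the effect of group clinics. The documents do not support that. The protocol nowhere specifies levels; the inference rests on the absence of any stated change contrast, and an SAP may supply one. The early indication of advantages promised at the end of the general principles rests on all the quantitative data together, including before/after at Newham. However, the conflict over purpose lies in the protocol itself. A later SAP also cannot create a matched baseline if definitions and windows were not aligned when the data were collected.

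A reader might also infer that both ends of a controlled before/after are already secured. That is not supported either. The formative items are given as examples and name no biological marker. The workstream 4 data collection section gives no timing for the external data. It also lists Barts Health sites more widely than the Royal London alone. No audit extract for the earlier period is described.

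The difference-in-difference bullet opens by comparing intervention patients with the 60 control data participants, whom the data collection section places at external units. The trajectories it then specifies are for accept versus decline, so it does not settle the unit-level contrast.

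Finally, drift of a few points at one hospital could decide the sign of a differenced result, and non-attendance may change meaning as appointment frequency changes, as the protocol itself warns. Both limit what any such contrast can show.

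**Conclusion.** The point holds as a conflict between sections with a practical consequence. The summary and the workstream 4 objective use benchmarking to indicate potential. The general principles and data analysis sections use it to describe units. No between-unit change contrast is stated, although a three-unit formative evaluation precedes implementation. Read with the summary and objective, a standing hospital difference could pass for benefit or harm.

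The size of the bias cannot be computed, because no outcome levels are given for the Royal London, the Whittington or the audit. The yardstick of about 3 percentage points in non-attendance rests on an assumed 25% relative fall among 80-100 of 214 patients and on equal appointments per patient. It scales in proportion to the assumed fall. The direction of the bias is unknown. The conflict between the sections does not depend on these assumptions.

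**What to change.** - **Summary, workstream 4 objective and workstream 4 data analysis:** base any statement about the potential of group clinics on the change at Newham minus the change at each comparator unit over the same period. Where an audit extract for the earlier period is available, also report it minus the change in the age-matched audit data.
- **Data collection:** re-extract the unit-level items of the formative evaluation (attendance or non-attendance and service-level outcomes) at Newham, the Royal London and the Whittington at the end of the evaluation. Use the definitions and calendar window of the first extraction, and name the same units both times.
- **Workstream 1:** reconcile the passages that place the formative evaluation at Newham only with the list of three units.
- **Keep** the level comparisons for every descriptive purpose already given: heterogeneity, case mix, characterising units and feasibility.
- **State the limit:** with one intervention unit and two comparators, the change contrast removes only stable differences and remains descriptive.

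The cost is rewording and one matched repeat extraction at units already expected to supply data. Differencing may lose some precision where before/after correlation is low.
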